15.4 Expectedness

The Chief Investigator (or another delegated appropriately qualified individual) will assess each SAR to perform the assessment of expectedness.

The expectedness assessment should be made with reference to the list of expected adverse events in Table 4. Expectedness decisions must be based purely on whether the event is listed. Other factors such as the participant population and participant history should not be taken into account. Expectedness is not related to what is an anticipated event within a particular disease. SARs which add significant information on specificity or severity of a known, already documented adverse event constitute unexpected events. Fatal and life-threatening SARs should not be considered expected.

The table below lists the expected adverse events with radiotherapy.

Table 5. Expectedness assessment

Intervention	List to be used for expectedness assessment
Radiotherapy	Graft failure. Bleeding considered related to the surgery or radiotherapy requiring hospital admission. Infection requiring i.v. antibiotics (where infection started in area of surgery or radiotherapy).

15.5 Reporting Procedures

15.5.1 Participating Site Responsibilities

The PI (or delegated medically qualified doctor from the trial team) should sign and date the SAE CRF to acknowledge that he/she has performed the seriousness and causality assessments. Investigators should also report SAEs to their own health boards or trust in accordance with local practice.

A completed SAE form for all events requiring immediate reporting should be submitted via secure email to the CTR within 24 hours of knowledge of the event. A separate form must be used to report each event, irrespective of whether or not the events had the same date of onset.

The participant will be identified only by trial number, month, and year of birth and initials. The participant's name (or any other personal identifiers) should not be used on any correspondence.

It is also required that sites respond to and clarify any queries raised on any reported SAEs and report any additional information as and when it becomes available through to the resolution of the event. Additionally, CTR/pharmaceutical companies may request additional information relating to any

SAEs/SARs and the site should provide as much information as is available to them in order to resolve these queries.

Serious Adverse Event (SAE) email address:

[contact]

Serious adverse events should be reported from time of randomisation, throughout the treatment period up to 4 months from randomisation. Serious adverse events relating to graft failure should be reported up to 12 months after randomisation. Serious adverse reactions (such as long-term side effects of trial treatment under investigation) should continue to be reported until the end of follow up as defined in the protocol.

Serious Adverse events (SAE) in oncology trials should be graded using the NCI Common Terminology Criteria for Adverse Events (CTCAE) Version 5.0.

An SAE form should contain at least the minimum information:

- Full participant trial number.
- An Adverse Event / Adverse Reaction.
- Trial intervention.
- A completed assessment of the seriousness, and causality as performed by the PI (or another appropriately medically qualified doctor registered on the delegation log).

If any of these details are missing, the site will be contacted, and the information must be provided by the site to the CTR within 24 hours.

All other AEs should be reported on the CRF following the CRF procedure described in Section 18.2.

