5.2 Secondary objectives

- To determine the impact on QoL of ART in completely resected high risk (BWH T2b/3) primary cSCC compared to standard clinical follow up.
- To evaluate distant metastasis-free survival in both groups.
- To evaluate overall survival (OS) in both groups.
- To determine the safety of ART in terms of the proportion of patients experiencing toxicity compared with close clinical follow up.
- To evaluate the cost-effectiveness of ART.

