5.4 Secondary outcomes measure(s)

- QoL – measured using EORTC QLQ C30, skin-specific Skin Cancer Index (SCI), and Picker Patient Experience 15 questionnaire (PPE-15) (4, 5).
- Distant metastasis-free survival, defined as days from randomisation to the date of distant metastasis or death from any cause.
- OS, defined as days from randomisation to death for any reason.
- Safety /toxicity as measured by common terminology criteria for adverse events (CTCAE) V5.0 scoring system and serious adverse events, including patient-reported outcomes version of the CTCAE.
- Cost-effectiveness determined by health utility using EQ-5D-5L and recording health resource use. Primary economic outcome, cost per quality-adjusted life year (QALY). Secondary economic outcome, resource use and costs (6).

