Toxicity assessment / AEs		x		x	x	x	x	x	x		x		x		x
Randomisation		x													
Pregnancy test (if applicable)		*	x												
QoL and HE Questionnaires ^{&}		x		*	*	*	x	x		x			x		x

[§]for participants randomised to receive ART

*for participants receiving 4 weeks of ART treatment

** for participants receiving 6 weeks of ART treatment

[&] EQ-5D-5L, Skin-specific Cancer Index, and EORTC QLQ-C30 , Picker Patient Experience 15 questionnaire. Please see additional table 2 for breakdown of questionnaires per hospital visit. Health Resource Utilisation should be completed in conjunction with the patient and a research nurse.

Table 2: Questionnaire administration per visit

						Time From Randomisation Date								
	Baseline	End of 2 weeks ART (for ART arm only)	End of 4 weeks ART (for ART arm only)	End of 6 weeks ART (for ART arm only)	Completion of ART (for ART arm only)	7 weeks (+/- 4 weeks) (for Non ART arm only)	4 Months	8 Months	12 Months	16 Months	20 Months	24 Months	30 Months	36 Months
EQ-5D	✓	*	*	*	✓	✓	✓	*	✓	*	*	✓	*	✓
EORTC QLQ-C30	✓	*	*	*	✓	✓	✓	*	✓	*	*	✓	*	✓
SCI	✓	*	*	*	✓	✓	✓	*	✓	*	*	✓	*	✓
PPE-15	*	*	*	*	*	*	*	*	✓	*	*	*	*	*
Patient Reported Toxicities	✓	✓	✓	✓	*	✓	✓	✓	*	✓	*	✓	*	✓
To be completed by Clinicians: Clinician Reported Toxicities	✓	✓	✓	✓	*	✓	✓	✓	*	✓	*	✓	*	✓
To be completed by research team (in conjunction with patient): Health Utilisation/ Economics	✓	*	*	*	✓	✓	✓	*	✓	*	*	✓	*	✓

Concomitant Medications	✓	*	*	*	✓	✓	✓	*	✓	*	*	✓	*	✓
-------------------------	---	---	---	---	---	---	---	---	---	---	---	---	---	---

15 Pharmacovigilance

Recording of serious adverse events (SAEs) must start from the time of randomisation and must be performed at least until 4 months after randomisation (or until 30 days following the last fraction of radiotherapy if later).

The Principal Investigator is responsible for ensuring that all site staff involved in this trial are familiar with the content of this section.

All SAEs must be reported immediately (and within 24 hours of knowledge of the event) by the PI at the participating site to the CTR PV and Safety Specialist unless the SAE is specified as not requiring immediate reporting (see section 15.2).

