15.5.2 The CTR responsibilities

Following the initial report, all SAEs should be followed up to resolution wherever possible, and further information may be requested by the CTR. Follow up information must be provided on a new SAE form.

The CTR should continue reporting SAEs until 4 months after randomisation. Graft failure should be reported as and SAE up to 12 months after randomisation.

Once an SAE is received at the CTR, it will be evaluated by staff at the CTR and sent to the Chief Investigator (or their delegate) for an assessment of expectedness.

Investigator reports of suspected SARs will be reviewed immediately and those that are identified as SUSARs are reported to the Research Ethics Committee.

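### After month 4 (month 12 for graft failure) serious events go on SAE forms only if possibly related to radiotherapy, so SAE counts by arm are comparable only within that window

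*Protocol*

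**What the plan says.** The safety objective in section 5.2 is comparative: "To determine the safety of ART in terms of the proportion of patients experiencing toxicity compared with close clinical follow up". Section 5.4 measures it with the CTCAE version 5.0 "scoring system and serious adverse events, including patient-reported outcomes version of the CTCAE". Serious adverse events are thus one component of a between-arm outcome.

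The reporting rules are in section 15:

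- **Opening of section 15:** SAE recording starts at randomisation and is to be "performed at least until 4 months after randomisation (or until 30 days following the last fraction of radiotherapy if later").
- **Section 15.5.1 (sites):** "Serious adverse events should be reported from time of randomisation, throughout the treatment period up to 4 months from randomisation". Then: "Serious adverse events relating to graft failure should be reported up to 12 months after randomisation". Serious adverse reactions, by contrast, "should continue to be reported until the end of follow up as defined in the protocol".
- **Section 15.5.2 (coordinating centre):** "The CTR should continue reporting SAEs until 4 months after randomisation", with graft failure again to month 12.
- **Table 3:** a serious adverse reaction is an SAE with a reasonable possibility of being related to radiotherapy.
- **Section 15.3, Table 4:** a rating of possible is enough to count as related, and the Chief Investigator cannot downgrade the site's rating.
- **Section 16.1:** the trial is open label.

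**The concern.** Closing all-cause SAE reporting after the treatment period while keeping reactions open is a usual choice for safety surveillance. The difficulty is that the same stream also feeds a comparative outcome. After month 4 an event other than graft failure reaches an SAE form only if someone links it to radiotherapy, and that condition depends on the allocated arm.

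The protocol's own list of trial-specific SAEs makes this concrete. Section 15.2 names serious infection starting in the surgical or irradiated area, and bleeding related to surgery or radiotherapy that leads to admission. Every participant has had surgery, so both arms are at risk, and Table 5 lists the same events as expected with radiotherapy. Such an event at month 10 is reportable as serious in an irradiated patient if judged possibly related. The same event in a comparator patient has no SAE route. The judgement is made with the arm known.

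At stake is the serious-event part of the safety conclusion. A count by arm over the whole of follow-up would set late events in the radiotherapy arm against almost none in the comparator arm, even if the true rates were equal.

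**Working it through.** The protocol gives no figure to reproduce. The check is arithmetic on the reporting windows.

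**Inputs**
- All-cause SAE reporting ends at month 4 (sections 15.5.1 and 15.5.2).
- Graft-failure reporting ends at month 12, with no relatedness condition and no arm restriction (same sections).
- Serious adverse reactions are reported to the end of follow-up (section 15.5.1).
- Follow-up is at least 3 years from randomisation (section 21), and the last scheduled visit is at 36 months (Table 1).
- Radiotherapy starts within one month of randomisation (section 14.2) and lasts 2, 4 or 6 weeks (synopsis).

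**What is reported on SAE forms, by period**

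| Months | Radiotherapy arm | Comparator arm |
|---|---|---|
| 0–4 | all SAEs | all SAEs |
| 4–12 | graft failure; radiotherapy-related SAEs | graft failure |
| 12–36 | radiotherapy-related SAEs | none, unless irradiated later |

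**Length of each gap**
- No all-cause SAE reporting: 36 − 4 = 32 months; 32/36 = 89%.
- Of these, graft failure is still reported in both arms for 12 − 4 = 8 months.
- Wholly one-sided: 36 − 12 = 24 months; 24/36 = 67%.

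**Does the 30-day clause lengthen the window in the radiotherapy arm?** With a month of 30.44 days, the latest start on schedule and the longest course give 30.44 + 42 + 30 = 102.4 days, or 102.4/30.44 = 3.4 months. That is before month 4. The clause passes month 4 (121.76 days) only if radiotherapy starts later than:
- 6-week course: 121.76 − 30 − 42 = 49.8 days, 1.6 months after randomisation
- 4-week course: 121.76 − 30 − 28 = 63.8 days, 2.1 months
- 2-week course: 121.76 − 30 − 14 = 77.8 days, 2.6 months

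The clause therefore bites only when radiotherapy starts later than section 14.2 allows. The difference from the flat 4 months is mainly one of wording, although the phrase setting month 4 as a minimum also leaves the end date open.

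**Direction and possible size of the artefact.** The documents give no late serious-event rate, so the following is an assumption. Let *b* be the rate of serious site infection or bleeding after month 4, equal in both arms, and *f* the share judged possibly related in irradiated patients. The reported rates are then *b* × *f* against about 0. With *b* = 2–5% and *f* = 50%, the result is 1–2.5% against about 0%. With 840/2 = 420 patients per arm, that is about 4 to 10 patients. Since *f* may lie anywhere from 0 to 1, the spurious difference ranges from 0 to the full 2–5%. Only its direction is firm.

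**The case against.** The strongest reply is that the harmful analysis is supposed, not planned. The objective speaks of the proportion of patients with toxicity. No section prescribes an SAE count pooled past month 4, and confining an SAE table to a common window is ordinary SAP content. This stands in part: the protocol cannot be said to plan a biased count. But it does make SAEs part of a comparative outcome, states no window for that comparison, and fixes a collection rule that differs in effect by arm. An SAP can limit the comparison; it cannot recover SAE forms that were never requested.

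Several stronger readings are tempting, and the documents do not support them.

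- *Reporting is one-sided for all 32 months after month 4.* Graft failure is itself a trial-specific SAE and is reportable in both arms to month 12. Full one-sidedness covers 24 months.
- *Late serious complications in the comparator arm go unrecorded.* Table 1 schedules examination of the surgical site at follow-up visits without arm restriction. Table 2 schedules clinician- and patient-reported toxicity in both arms at 8, 16, 24 and 36 months. Section 15.5.1 sends other adverse events to the CRF, section 12 collects hospital stays as resource use, and deaths enter overall survival. What is missing is a like-for-like SAE form.
- *The comparator count is zero by construction.* Table 3 covers any trial participant, and section 4 notes that recurrence is treated with surgery, radiotherapy or both. A comparator patient irradiated for recurrence might qualify, so the count is essentially zero but not guaranteed to be.
- *The 30-day clause routinely gives the radiotherapy arm a longer window.* On schedule it does not, as shown above.

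**Conclusion.** The point holds in this form: SAE counts by arm are comparable to month 4, and for graft failure to month 12, but no further. All-cause SAE reporting is absent for 32 of 36 months, and what remains is wholly one-sided for 24 of 36. These figures follow from the stated windows and a 36-month schedule; the statement that the comparator arm yields almost no serious reactions assumes that few of its patients are irradiated later.

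A whole-trial SAE comparison would be biased against radiotherapy. The size of that bias cannot be derived from the protocol, and the illustration above rests on assumed rates. The primary endpoint, the power and the late toxicity comparison are unaffected. The differing end dates in section 15 are a separate inconsistency and need correcting in any case. The matter deserves a change because the outcome is comparative and the remedy needs no new data.

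**What to change.** 1. In section 5.4 and section 15, state that the between-arm SAE comparison runs from randomisation to one common end date in both arms: month 4 for all SAEs, month 12 for graft failure.
2. State that serious adverse reactions reported after that window are described only and are not entered in a between-arm SAE count.
3. Name the clinician- and patient-reported toxicity in Table 2 (8, 16, 24 and 36 months, both arms) as the basis for the late between-arm safety comparison. Section 14.3 prints 26 months where Tables 1 and 2 have 36; align them, since this comparison depends on that visit.
4. Reconcile the opening of section 15, which makes month 4 a minimum and adds "or until 30 days following the last fraction of radiotherapy if later", with the flat 4 months in sections 15.5.1 and 15.5.2. Whatever reporting period is kept for surveillance, the comparison window should not depend on the date of the last fraction, which only one arm has.

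The cost is protocol and SAP wording, with no new data collection. The downside is that no randomised comparison of SAEs is claimed after the common window. The present reporting rule could not support one.

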15.5.2 The CTR responsibilities

Following the initial report, all SAEs should be followed up to resolution wherever possible, and further information may be requested by the CTR. Follow up information must be provided on a new SAE form.

The CTR should continue reporting SAEs until 4 months after randomisation. Graft failure should be reported as and SAE up to 12 months after randomisation.

Once an SAE is received at the CTR, it will be evaluated by staff at the CTR and sent to the Chief Investigator (or their delegate) for an assessment of expectedness.

Investigator reports of suspected SARs will be reviewed immediately and those that are identified as SUSARs are reported to the Research Ethics Committee.

15.6 SUSAR reporting

Cardiff University is undertaking the duties of trial Sponsor and has delegated to the CTR the responsibility for reporting SUSARs and other SARs to the relevant ethics committees) as follows:

SUSARs which are both fatal or life-threatening and not fatal or life-threatening must be reported to the REC within 15 calendar days of receipt at the CTR.

If the report is incomplete then additional follow-up information should be reported within a further 8 calendar days of submitting the initial report, for all fatal and non-fatal, life-threatening, and non-life threatening.

Any additional, relevant information must be reported within a further 15 days.

15.7 Safety Reports

A list of all SAEs (expected and unexpected) will be reported annually to the trial sponsor.

15.8 Contraception and pregnancy

15.8.1 Contraception

The majority of patients will fall outside of being of childbearing potential or are the partner of such a person. For participants who are of childbearing potential, they should follow local standard of care regarding contraception as long as this a highly effective form of contraception. Note, Radiotherapy has a demonstrated human teratogenicity/fetotoxicity.

15.8.2 Pregnancy reporting whilst participating in the trial

Pregnancy, or the pregnancy of a partner occurring whilst participating in the trial, is not considered an SAE, however, a congenital anomaly or birth defect is. Other cases (e.g., termination of pregnancy without information on congenital malformation, and reports of pregnancy exposure without outcome data) should not normally be reported as such. When pregnancy occurs in a trial, either in a female participant or the female partner of a male participant, this should be followed up until at least the end of pregnancy, whether that is a live birth, abortion etc. Without follow-up of the pregnancy, it would not be possible for the CTR to know if a congenital anomaly or birth defect occurred, and therefore if there was an SAE that must be included in the safety evaluation of the radiotherapy. Information on a pregnancy in a trial participant will be captured on the CTR Pregnancy Report Form supplied to sites by the CTR.

Sites should report pregnancy occurring within SAE reporting periods stipulated in this trial protocol. Congenital anomalies or birth defects are considered an SAE and so these events must also be

reported to the CTR on a trial-specific SAE form. The CTR will report this within as a SUSAR 15 days to the Ethics Committee.

15.9 Urgent Safety Measures (USMs)

An urgent safety measure is an action that the Sponsor, Chief Investigator or Principal Investigator may carry out in order to protect the subjects of a trial against any immediate hazard to their health or safety. Any urgent safety measure relating to this trial must be notified to the Research Ethics Committee immediately by telephone, and in any event within 3 days in writing, that such a measure has been taken. USMs reported to the CTR will be handled according to CTR processes.

16 Statistical considerations

The design is two-arm group-sequential phase III trial, with a time to event outcome of locoregional recurrence-free survival and two formal interim analysis after 77 and 115 events and a final analysis. A group sequential design was selected due to the large effect size that we hope to detect and provides the potential to make cost savings by stopping the trial early in the event of a large enough effect size at either of the two interims. LRR free survival was considered the most important endpoint because LRR causes mortality, significant morbidity and reduces quality of life. The trial also includes a SWAP to address recruitment issues in this underserved population.

16.1 Randomisation

Participants recruited should be randomized to each group with a fixed ratio of 1:1 using a centralized internet randomization. Randomisation will be by minimisation with a random element. Randomisation stratification factors will be; age category, stage of cancer, immunocompromised, time since surgery and perineural invasion. The trial is open-label since participants in the intervention arm will receive radiotherapy.

16.2 Sample size

Assuming a conservative LRR of 20% for T2b and 50% for T3 cSCC (16, 17), and UK data confirm 92% of recurrence is within 3 years (14). Our extensive SSMDT and PPI work support a 35% reduction as a meaningful clinical effect in LRR as justification for use of ART (26, 27). This plausibility of this effect size is also supported by a recently published observational study (24). For the primary outcome to improve LRR-free survival from the current rate of 80% to 87% at 3 years (reduction in LRR events of 35%) translates into a hazard ratio of 0.624. In absolute terms, for a LRR of 20 out of 100 recurrences, 35% reduction translates to 7 fewer recurrences.

The sample size was calculated based on the time-to event outcome of LRR free survival, using the armenu package in Stata 17. With the expected 3-year LRR-free survival of 0.8 in the standard clinical

follow up arm, and a HR of 0.624, with 1:1 allocation ratio and applying a two-sided type I error rate of 5% and 90% power, 194 events are required for analysis of the primary outcome. Recruiting 752 patients over 4 years with these assumptions predicts that this number of events will be observed after approximately 3 years follow-up. Allowing for 10% dropouts (loss to follow up, withdrawals, deaths from other causes – all censored observations), and rounding up slightly, the total sample size required is 840 patients.

We will use competing risks regression to account for death from other causes or distant metastasis events prior to local recurrence. Because most of these events will be due to death from other causes rather than distant metastases, we do not expect this to be more than the 10% we have allowed for attrition. However, if competing events are seen to be higher than expected during trial monitoring, we will discuss with the funders about the possibility of recruiting more patients to achieve the target number of LRR events.

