17.1 Main analysis

The trial will be analysed when at least 194 events have been reported.

Patients that withdraw completely or are lost to follow-up will be censored at the date last known to be recurrence free and patients that die due to other causes will be censored at the time of death.

A full statistical analysis plan will be finalised prior to the first formal analysis of this group sequential trial. The primary analysis is the stratified logrank test. The design will include two formal interim analyses after 77 and 115 events (appx. 600 and 760 randomised), allowing the trial to stop early if, at each formal interim analysis the log-rank test statistic is larger than +/- 3.36 and +/- 2.68 respectively. Stopping for efficacy at either interim analysis would mean fewer participants need to be recruited and follow-up can be reduced for the remaining patients. If the test statistic is not large enough at the interim analyses, the trial will continue to the full target, and will be analysed when at least 194 events have been reported. The log-rank test will be significant if the final test statistic is greater +/- 1.98 (45). The total alpha spent in all 3 analyses adds up to 5%. We will actively monitor recruitment (LRR event rates, dropout rates) to project when the necessary number of events might occur. This will allow timely recruitment adjustments if needed. Recruitment projections are based on 100 patients in year 1, 200 in year 2, 240 in year 3 and 300 in year 4. Alternative study lengths and recruitment periods were considered; this was found to be the most realistic in ensuring recruitment to the required sample size in the shortest overall duration.

If proportional hazards assumptions are not violated, then a Cox regression model will be used to estimate the hazard ratio for the primary outcome and for secondary outcomes of distant metastasis-free survival and overall survival, adjusted for prognostic factors. If the proportional hazards model is strongly violated, then restricted mean survival analysis methodology will be used for multivariable analysis.

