Interviews with patients and staff will be recorded directly by the qualitative researcher using processes for secure data capture and storage in line with University of Bristol procedures (as outlined on the University of Bristol website). Recordings will be held on a secure drive with restricted access at the University of Bristol for long-term storage and analysis. Recordings will be labelled with the SCC-AFTER participant identification number by the Bristol team; identifiable patient details will not be used. At the end of the trial, recordings will be held for a minimum of 15 years after which they will be destroyed.

Participants will not be identifiable in reports produced to describe the QRI findings at the end of the study.

QRI documentation

Paper or electronic documentation which is generated through the process of performing the QRI will be stored securely at the University of Bristol with access restricted only to approved personnel.

19 Translational research or sub trial

There is no current funding for a translational sample collection, although a number of areas around tumour characteristics and response to treatment would provide valuable information relating to treatment of the disease.

Consent will be collected to use the surgical sample (or biopsy) collected as routine standard of care by NHS sites, for future translational use and this collection will be made when funding is secured.

20 Protocol/GCP non-compliance

The Principal Investigator should report any non-compliance to the trial protocol or the conditions and principles of Good Clinical Practice to the CTR in writing as soon as they become aware of it.

21 End of Trial definition

The treatment phase will be followed by a follow-up period which will continue for a minimum of 3 years from time of randomisation. Progression/death data for all patients will continue to be collected until the last patient has completed 3 years.

The end of the trial is defined as the date of final data capture to meet the trial endpoints. In this case end of trial is defined as the final follow-up collection, which will be at least 3 years after final patient is randomised.

Sponsor must notify the REC of the end of a clinical trial within 90 days of its completion or within 15 days if the trial is terminated early.

22 Archiving

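### The projection of 194 events from 752 patients needs a constant recurrence hazard to year 7, which conflicts with the 92%-within-3-years figure in the same paragraph; the final analysis has no calendar fallback

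*Protocol*

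**What the plan says.** Section 16.2 sets the target effect as "to improve LRR-free survival from the current rate of 80% to 87% at 3 years", which "translates into a hazard ratio of 0.624". It then says that, "applying a two-sided type I error rate of 5% and 90% power, 194 events are required for analysis of the primary outcome". On timing it says: "Recruiting 752 patients over 4 years with these assumptions predicts that this number of events will be observed after approximately 3 years follow-up". A 10% allowance takes 752 to 840.

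The opening of the same paragraph gives LRR as 20% for T2b and 50% for T3, without the stage mix, and adds that "UK data confirm 92% of recurrence is within 3 years".

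Section 17.1 projects accrual of 100, 200, 240 and 300 patients in years 1 to 4. It sets boundaries of 3.36 at 77 events, 2.68 at 115 events and 1.98 at the final look, and says: "The trial will be analysed when at least 194 events have been reported". The synopsis and sections 6 and 16.5 repeat that trigger, and none gives a calendar alternative. Section 21 says: "Progression/death data for all patients will continue to be collected until the last patient has completed 3 years".

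**The concern.** If 20% of controls recur by 3 years and that is 92% of all who ever will, few events remain for years 3 to 7. The projection nevertheless draws more than a third of its events from that period. Either the hazard assumption behind 194 or the 92% figure must give way.

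The stated 90% power depends on 194 events being reached. If they come late or not at all, the protocol gives no rule for when the final analysis takes place or which critical value applies.

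**Working it through.** **Inputs.** From 16.2: LRR-free survival 0.80 and 0.87 at 3 years, HR 0.624, 1:1 allocation, 752 evaluable patients (840 in total), 4 years' accrual plus about 3 years' follow-up, 92% of recurrence within 3 years. From 17.1: the accrual pattern and boundaries.

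**1. Reproducing the plan.**
- HR = ln 0.87 / ln 0.80 = 0.624.
- Events for 90% power: 189 (Schoenfeld) or 197 (Freedman), so 194 is reasonable. With the stated boundaries at 77, 115 and 194 events, two-sided alpha is 0.050 and power 90.5%.
- Constant hazards: −ln(0.80)/3 = 0.0744 and −ln(0.87)/3 = 0.0464 per year.
- With uniform accrual over 4 years and a cut at year 7, follow-up runs from 3 to 7 years. The mean event probability is 1 − (e^(−3λ) − e^(−7λ))/(4λ), that is 0.3080 (control) and 0.2060 (ART). Events = 376 × (0.3080 + 0.2060) = 193.
- 752/0.9 = 836, rounded to 840.

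The plan's figure is therefore recovered.

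**2. What that model implies.** Control LRR at 7 years is 1 − e^(−7 × 0.0744) = 40.6%, so only 0.20/0.406 = 49% of the control recurrences by year 7 fall within 3 years. Events within each patient's first 36 months are 376 × (0.20 + 0.13) = 124. The other 69 of 193 (36%) come later, where the 92% figure leaves 8%.

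**3. Using the 92% instead.** Every patient has at least 3 years by year 7, so the count lies between events by month 36 and the eventual ceiling, whatever the curve's shape:

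| | by month 36 | at year 7 | ceiling |
|---|---|---|---|
| 752 patients | 124 | 131-132 | 752 × 0.165/0.92 = 135 |
| 840, no losses | 139 | 146-147 | 840 × 0.165/0.92 = 151 |

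The year-7 column takes control incidence F(t) = (0.20/0.92)(1 − e^(−0.842t)), where 0.842 = −ln(0.08)/3, and ART incidence 1 − (1 − F)^0.624. The lower value in each cell uses the stated accrual, the higher uses uniform accrual.

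**4. Power at those counts** (HR 0.624, interims at 77 and 115). With 1.98 kept at the final look, power is 74% at 124 events, 76% at 131, 78% at 135, 81% at 147 and 82% at 151. The two interims use about 0.0076 of the 0.05. If all the rest is spent at the final look, the critical value is about 1.96 at 124 events and 1.97 at 150, and power at 131 to 147 events is 77.0% to 81.5%.

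**5. Constant hazard with the stated accrual.** Scaling 100/200/240/300 to 752 gives 181 events at year 7 (88% power), and 194 at about year 7.4.

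**6. What monitoring would show** (840 patients, no losses, stated accrual):

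| Year | constant hazard | 92% pattern |
|---|---|---|
| 3 | 38 | 55 |
| 4 | 76 | 96 |
| 5 | 121 | 127 |
| 6 | 163 | 141 |
| 7 | 202 | 146 |

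Events run ahead of projection until after recruitment closes at year 4, then plateau.

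**The case against.** A reader might infer that 194 events cannot arise at all. The documents do not support that. The 80% control rate equals the T2b rate alone, which 16.2 calls conservative, while T3 patients at 50% are also eligible. With the 92% kept as a ceiling and rates of 20% and 50%, 194 is reached at a T3 share of about 20% of 840 without losses, or about 29% of 752. With the 30% T2b rate given in section 4, 752 patients yield about 205 events with no T3 at all. This stands as a limit on the claim. It does not rescue the calculation, which uses 0.80 and states no T3 share.

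A reader might also infer that the final analysis will never happen. That goes too far. Section 17.1 plans monitoring of event rates with recruitment adjustments, and section 21 makes 3 years a minimum, with progression data collected on all patients beyond their own month 36. But step 6 shows that monitoring would give little warning while recruitment could still be adjusted. Section 16.2 raises extra recruitment only for excess competing events, of which it says "we do not expect this to be more than the 10% we have allowed for attrition".

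Low power and a missed trigger are alternatives: if the analysis waits for 194 events, power is about 90%; the 77-81% applies only if it takes place at year 7 with fewer.

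Finally, the 92% may not be a lifetime share. The title of its cited source concerns metastatic disease, and the length of follow-up behind the figure is not given. The ceiling is therefore conditional on reading 92% as a share of all recurrences.

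**Conclusion.** Wrong as written. HR, event requirement and dropout inflation are arithmetically sound. The fault is that the prediction of 194 events rests on an unstated constant hazard, which the 92% figure in the same paragraph contradicts. On the 80%/87% rates and the 92%, expect about 131 to 147 events at year 7 and power of about 77-81%, against the stated 90%. Even under a constant hazard, the protocol's own accrual gives about 181 events at year 7.

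These figures assume HR 0.624, the 92% as a share of all recurrences, and either 752 evaluable patients or 840 with no losses. A higher control rate would improve them. Because the trigger is events only, the final analysis may be delayed or missed.

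**What to change.** 1. In section 16.2, state the hazard shape, T3 share and accrual pattern used, and reconcile them with the 92%. Then restate expected events and power: about 131-147 events and 77-81% on the 80%/87% and 92% figures. Alternatively, justify a constant hazard, saying that about 36% of events must then arise after month 36, or justify a higher control rate.
2. In the synopsis and sections 6, 16.5 and 17.1, add a calendar backstop to the 194-event trigger, at the end-of-trial follow-up point in section 21. State that all remaining alpha is spent at that final look, with the critical value recomputed from the alpha used at 77 and 115 events (about 1.96-1.97 for 124-150 events). This must be explicit because the protocol names no spending function.

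The cost is protocol and SAP wording, and a less favourable stated power if the backstop applies. Correcting the statement needs no extra patients. Whether to accept that power or enlarge the trial is the sponsor's decision.
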